#### *Research question:*

- 1. What is de the difference in the proportion of study patients seen by the GP between intervention and control weekends?
  - 1.1. Is this proportion associated with the patient's presentation (chosen eMTS flowchart and urgency)?
  - 1.2. Is this proportion associated with the occupancy rate of the ED and/or GPC?
  - 1.3. Is this proportion associated with the operating triage-nurses and/or the operating emergency physician?
  - 1.4. Is this proportion associated with the patient's background characteristics? (sex, age, community, insurance status)?
  - 1.5. Is there seasonal variation in this proportion?

Secondary hypothesis: a nurse using the eMTS is able to detect primary care patients. We can assess the correctness of the nurse's allocation advice as a diagnostic instrument.

The results of the triage consult is either a GPC or ED advice. Arbitrarily we will call a GPC advice a positive diagnosis. The gold standard is the opinion of the physician (either emergency physician or GP) after the consultation. This standard is used in almost all of the literature(3), as no better gold standard is available. We are aware of some disadvantages: this opinion depends on the personality and other characteristics of the treating physician and some patients have presentations suitable for both ED and GPC. On the other hand, agreement between nurse and physician is important for the feasibility of extended triage.

The way we will measure the correctness of the triage advice depends on whether the patient is compliant to this advice. This makes Table 1 more complex:

	Patient goes to GPC		Patient goes to ED	
Opinion physician	GPC correct	Had to go to ED	ED correct	Had to go to GPC
Advice GPC	Correct decision 1	False positive 1	False positive 2	Correct decision 2
Advice ED	False negative 1	Correct decision 3	Correct decision 4	False negative 2

Table 2: patient categories for the eMTS as a diagnostic instrument

Because our eMTS is risk adverse, we already know we will have a certain amount of false negative 2: patients who are compliant to the advice of ED although they had to go to the GPC according to the emergency physician. This category is not our primary focus.

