We are mostly interested in false positive 1: patients who complied with the advice GPC but should have stayed at the ED. Some of these patients might be subject to a safety risk. For example, a patient with a heart attack allocated to the GPC might lose valuable time. This category is the same as the proportion of study patients allocated to the GP but referred back to the ED. We will give this category special attention in our process analysis.

Finally, we are also interested in the category correct decision 2: patients who are not compliant to a correct GPC advice. These patients made an inefficient decision so there is room for improvement.

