# Methodology for the medical aspect

The data necessary for this work package are part of a routine clinical report. We will use three types of these reports: triage-consultation reports, ED consultation reports and GPC consultation reports. We will collect these data using the iCAREdata database. This database can link our three types of clinical reports using an irreversibly coded national number. Due to data protection rules, the iCAREdata data manager will execute all queries and only aggregated results will be transferred to the researchers. For more complex statistical analysis, the data manager will transfer an analysis specific table or the analysis will be carried out on the computer of the data manager in cooperation between the researcher and the data-manager. A detailed data management plan is available. The correctness of a triage decision depends on the patient's situation:

- At the GPC (patients compliant to a GPC advice or non-compliant to an ED advice): the ratio of patients referred to an ED to the total number of patients coming from the ED of AZ Monica.
- At the ED (patients compliant to an ED advice or non-compliant to a GPC advice): the physician will answer the same question for all patients: "Should this patient better go to the GPC?". The correctness is defined as the ratio of the patients with a positive answer to this question to the total number of patients staying at the ED after triage.

The parameters of interest in questions 1 through 8 are (conditional) proportions, which calls for analysis by a non-linear model (e.g. binary logistic regression). The study design results in the creation of nested data, where patients are nested in weekends, and weekends are nested in (multiple) nurses. Appropriate analysis of such auto-correlated data requires a nonlinear mixed model. During the first months, data will be used to produce point-estimates of these proportions (e.g., patients seen by GP, correct triage decisions, all false positives, type 1 false positives, patients left without being seen, etc.). With increasing duration of the study, incoming data will be used to explain variability of these probabilities in terms of patient background characteristics, operating nurses/emergency physician, season, etc. Statistical assistance will be called for in order to conduct these analyses.

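### False positive 1 is defined by the GP's opinion but measured by referral, and the GPC referral ratio also pools patients who had been advised to stay at the ED

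*Combined protocol and SAP*

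**What the plan says.** The secondary hypothesis, in section 4 (Hypotheses and Research questions), treats the nurse's advice as a diagnostic test with GPC advice as the positive result. The reference standard is explicit: "The gold standard is the opinion of the physician (either emergency physician or GP) after the consultation". Table 2 crosses advice, destination and that opinion. False positive 1 is the cell with GPC advice, patient at the GPC, and a physician who thinks the patient belonged at the ED.

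The protocol gives this cell priority on safety grounds: "We are mostly interested in false positive 1: patients who complied with the advice GPC but should have stayed at the ED". Shortly afterwards it states: "This category is the same as the proportion of study patients allocated to the GP but referred back to the ED".

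Methodology for the medical aspect then describes two measures of correctness:

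- The GPC measure covers "At the GPC (patients compliant to a GPC advice or non-compliant to an ED advice". It is the number referred to an ED, divided by all patients who came over from the hospital's ED.
- At the ED, the physician answers a direct question for every patient on whether the GPC would have been the better place.

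No corresponding question to the GP is described. Research questions 2.1 (advice against the physician's evaluation) and 2.2 (referrals among patients with GP advice) are listed as separate items. Question 2.3 asks for all false positives and question 2.4 for type 1 alone.

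**The concern.** A judgement and an action are presented as one quantity. A GP may think that a patient belonged at the ED and still not refer, for example because the problem was dealt with on site or the patient declined. Under the referral measure that patient falls into correct decision 1. Conversely, a referral may follow a GPC visit that the GP regards as appropriate, and it is then counted as a triage error.

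The GPC ratio has a second fault. A patient who was advised to stay at the ED, went to the GPC anyway and was referred is correct decision 3 in Table 2. The ratio puts that patient in the same numerator as the false positives. It is also presented as a measure of correctness, although referral after GPC advice marks an incorrect decision.

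This is the diagnostic category that the protocol singles out, and safety monitoring is one of the stated reasons for a full year of data (Sample size). It needs one definition, one numerator and one denominator.

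**Working it through.** The plan states no rate, precision or sample size for false positive 1, so there is no figure to reproduce. The check is mainly one of definitions.

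**Step 1: the definitions side by side.**

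| Place | Group | Event counted |
|---|---|---|
| Table 2 | GPC advice, went to GPC | GP's opinion that the patient belonged at the ED |
| Text after Table 2 | Allocated to the GP | Referred back to the ED |
| Question 2.2 | GP advice | Referral |
| Methodology for the medical aspect, GPC measure | All who came from the ED, either advice | Referred to an ED |

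Group, event and destination (the study ED or any ED) all vary.

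**Step 2: when referral equals the Table 2 cell.** Among patients who complied with GPC advice, let p be the true proportion of false positive 1, s the share of these who are referred, and f the share of the others who are referred. Then

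referral proportion = p·s + (1 − p)·f.

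This equals p only if s = 1 and f = 0, or if the two errors happen to cancel. With p = 5% (assumed):

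| s | f = 0 | f = 2% |
|---|---|---|
| 1.0 | 5.0% | 0.05 + 0.95×0.02 = 6.9% |
| 0.8 | 4.0% | 0.04 + 0.019 = 5.9% |
| 0.5 | 2.5% | 0.025 + 0.019 = 4.4% |

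The reading can be too low or too high.

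**Step 3: patients involved (illustration).** From the documents: 8,000 weekend presentations in 2016 (Recruitment strategy), 15 exclusions per weekend (Inclusion and Exclusion), and one control weekend per four intervention weekends (Design of the clinical trial), read here as 80% intervention. So 8,000 − 15×52 = 7,220 patients, of whom 0.80×7,220 = 5,776 fall in intervention weekends. If 10% go to the GPC (assumed), n = 578 and p = 5% gives 28.9 patients. Referral would miss 28.9×0.2 = 5.8 of them at s = 0.8, and 28.9×0.5, or about 14, at s = 0.5. At f = 2% it would add 578×0.95×0.02, or about 11, who are not false positives. Over GPC shares of 5 to 20%, p of 2 to 10% and s of 0.5 to 0.8 (all assumed), the number missed runs from about 1 to about 58 a year.

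**Step 4: the pooled ratio.** Let w be the share of GPC arrivals who had ED advice. Assume that 5% are referred among those with GPC advice and 50% among those with ED advice. The ratio is (1 − w)×5% + w×50%:

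- w = 2%: 4.9% + 1.0% = 5.9%
- w = 5%: 4.75% + 2.5% = 7.25%
- w = 10%: 4.5% + 5.0% = 9.5%

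The whole excess over 5% comes from referrals of patients whose ED advice was supported.

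**Step 5: consequences for the research questions.** Question 2.3 adds false positive 1 (by referral) to false positive 2 (by the ED physician's opinion), which mixes two standards. Question 2.1 has no stated opinion data for GPC patients. Question 2.4 does not say which measure applies.

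**The case against.** The strongest reply is that referral is a disclosed operational measure. The protocol says: "The way we will measure the correctness of the triage advice depends on whether the patient is compliant to this advice". It then specifies referral for the GPC. Referral is the GP's judgement put into action and is available from routine reports. This stands: nothing was switched covertly, and referral is a reasonable proxy. But the protocol claims identity, does not discuss the proxy's limits, and elsewhere lists opinion and referral as two questions.

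A second reply is that question 2.2 already confines referrals to GP advice, and that the group going to the GPC against ED advice is expected to be small (Hypotheses and Research questions, Medical aspect). That limits the harm from pooling. It does not make the ratio in the methodology section correct as written.

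Two stronger readings are tempting, and the documents support neither.

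- A reader might infer that the referral measure hides the most dangerous patients, those whose need the GP did not recognise. The opinion standard would miss them too, because a GP who sees no need for the ED would say so. The loss specific to referral is narrower: patients judged to belong at the ED but not referred.
- A reader might infer a known undercount by treating unreferred ED returns within two weeks as missed false positives. Table 2 does not define the category by return, a return may reflect progression or a new problem, and question 8 already reports returns for each Table 2 category.

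Nor does safety rest on this count alone. Incident analysis is planned, and the process aspects are left to a separate protocol.

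**Conclusion.** The inconsistency holds. False positive 1 is defined by the GP's opinion, declared identical to referral, and served at the GPC only by a referral ratio over a wider group. The pooled ratio is wrong as written if it is used for false positive 1, because it counts supported ED advice as error. The missing GP opinion item is a weakness that is cheap to remedy.

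Neither the size nor the direction of the bias can be derived from the documents. The figures above rest on assumed values of p, s, f, w and the GPC share, and show only that the gap may be negligible or may be comparable with the rate itself. The primary comparison, the proportion of patients seen by the GP, is unaffected. The point deserves correction because it concerns the diagnostic category to which the protocol gives most weight.

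**What to change.** 1. Compute false positive 1 only among patients with GPC advice who went to the GPC. Report patients who went there against ED advice separately, and stop describing the pooled referral ratio as correctness.
2. Add to the GPC report the mirror of the ED question, asking whether the patient would have been better placed at the ED. Define false positive 1 from the answer, so that questions 2.1, 2.3 and 2.4 rest on one standard.
3. Replace the claim of identity with a statement that referral is a proxy. Report it under question 2.2, with one stated destination (the study ED or any ED).
4. Use the two-week ED returns already planned under question 8 as a sensitivity check for need that was not recognised at the visit, without relabelling returns as false positives.

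Items 1, 3 and 4 need only wording and use data already planned. Item 2 costs one extra item in the GPC report, which the documents describe as routine, so the effort of adding it has to be confirmed. Some GP answers will be missing. Their number should be reported, with referral as the stated fallback.

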#### *Research questions:*

- 2. What is the validity of the eMTS as a preliminary diagnostic instrument to detect a primary care patient?
  - 2.1. What is the proportion of correct extended triage decisions measured by comparing the triage advice with the urcenty evaluation of the physician?
  - 2.2. What is the proportion of correct extended triage decisions with advice GP measured by the proportion of referrals within this category?
  - 2.3. What is the proportion of patients wrongly assigned to GPC (all false positives)?
  - 2.4. What is the proportion of patients wrongly assigned to GPC who did go to the GPC (type 1 false positives)
- 3. What is the proportion of patients who are not compliant to a correct GPC advice (Correct decision 2).
  - 3.1. What are the determinants for this non-compliance? (same determinants as studied in question 1.1-1.4)
- 4. What is the proportion of patients in which the nurse gives another advice comparing to the eMTS?
- 5. Does the intervention influence the number of patients left without being seen?
- 6. What is the shift in workload during the different phases of this study for all participating healthcare providers (GPs, triage nurses and ED physicians)?
- 7. Does the epidemiology in terms of reasons for encounter and diagnoses at both OOH services differ between intervention and control weekends?
- 8. What is the proportion of patients who return to the ED within two weeks for each of the categories described in table 2?

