#### **eMTS**

The Manchester Triage System (MTS) is one of the most commonly used triage systems in Europe(1). It enables nurses to assign a clinical priority to patients, based on presenting signs and symptoms, without making any assumption about the underlying diagnosis. The MTS assigns patients to one out of five urgency categories, which determine the maximum time to first contact with a physician (2). In the TRIAGE-trial, we will use an extended MTS (eMTS): we did not change the MTS but added some extra questions to allow allocation to ED or GPC. Because of legal and practical reasons, we have decided to allow allocation to primary care only for the two lowest urgency categories. The patients in the green category (called standard urgency) have to see a doctor within two hours. For the blue category (called non-urgent) the maximum period is four hours. In Figure 1, we demonstrate the eMTS flow chart for shortness of breath in children.

Figure 1: eMTS flow chart for shortness of breath in children. The orange arrows and boxes are the extension.

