# 4 Research Approach

## A diagnostic Intervention

A nurse will see the patient ideally within ten minutes after arriving at the ED. The nurse will classify a patient's presentation using the MTS, which will enable to make a categorisation of urgency. If the patient's urgency category is either blue or green, the nurse will use the eMTS to assess suitability for primary care. This assessment depends on the presentational flow chart used: for some flowcharts, all or none of the blue/green presentations will be referred to primary care, for others the nurse has to ask additional questions. The result of this extended triage is a shared decision of the patient and the nurse: the patient is (or is not) eligible for primary care. Because not all possible questions and signs are incorporated in the eMTS the triage nurses will have the possibility to overrule the eMTS advice in both directions. An adapted registration system will help the nurse select and follow the correct flowchart and will give an eMTS advice once all questions have been assessed. Patients will have the right to refuse the advice of the nurse without any further consequences for their treatment at the ED. We will provide all participating nurses and physicians with a detailed manual in Dutch about the intervention and the research protocol. Our entire eMTS is also available as a separate file.

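### Question 2.1 scores the triage advice against the physician's urgency evaluation, whereas Table 2 and the methods section score it by the appropriate service

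*Combined protocol and SAP*

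**What the plan says.** Under Hypotheses and Research questions, question 2.1 asks for the proportion of correct extended triage decisions, "measured by comparing the triage advice with the urcenty evaluation of the physician" (the misspelt word is evidently urgency).

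The text introducing the secondary hypothesis sets the reference: "The gold standard is the opinion of the physician (either emergency physician or GP) after the consultation". That sentence does not say what the opinion is about, but Table 2 does. Its columns record whether the GPC or the ED was the right place, and the text below it describes patients who followed ED advice "although they had to go to the GPC according to the emergency physician".

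Methodology for the medical aspect makes this operational. At the ED the physician answers one question for every patient: "Should this patient better go to the GPC". At the GPC the measure is "the ratio of patients referred to an ED to the total number of patients coming from the ED of AZ Monica". Both concern the service; neither is an urgency rating.

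Two further sections link urgency to allocation. The eMTS section says "we have decided to allow allocation to primary care only for the two lowest urgency categories". A diagnostic Intervention says that, once the category is blue or green, "the nurse will use the eMTS to assess suitability for primary care", and that "for some flowcharts, all or none of the blue/green presentations will be referred to primary care". Other flowcharts need extra questions, and the nurse may overrule the result in either direction.

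**The concern.** Question 2.1 names a reference that the rest of the plan does not use. Urgency and suitability for primary care are separate here: the eMTS assesses suitability after urgency has been settled as blue or green, and some of those patients are meant to stay at the ED. Agreement with an urgency rating is therefore not the same as agreement on the right service.

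Question 2.1 gives the overall correctness figure for the secondary hypothesis. Questions 2.3, 2.4 and 3 rest on Table 2 categories, so a 2.1 computed on urgency could not be reconciled with them. The iCAREdata data manager runs the queries and passes mainly aggregated results to the researchers, so the reference actually applied might not be visible in the output.

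**Working it through.** The protocol gives no target or expected value for the proportion of correct decisions, so there is no figure to reproduce. The check sets the definitions side by side.

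**Step 1: is urgency equivalent to service?** The eMTS section makes blue or green a condition for GPC allocation. A diagnostic Intervention shows that the condition is not sufficient, since some flowcharts send no blue or green patients to primary care. The two references can therefore disagree by design.

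**Step 2: what could an urgency reference do to each Table 2 cell?** This needs a mapping. Assume, for illustration only, that a low urgency rating by the physician means GPC and a higher rating means ED. The protocol states no such rule.

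| Table 2 cell | Advice | Table 2 score | If rated low urgency | If rated higher urgency |
|---|---|---|---|---|
| Correct decision 1 (CD1) | GPC | correct | correct | error |
| False positive 1 (FP1) | GPC | error | correct | error |
| False positive 2 (FP2) | GPC | error | correct | error |
| Correct decision 2 (CD2) | GPC | correct | correct | error |
| False negative 1 (FN1) | ED | error | error | correct |
| Correct decision 3 (CD3) | ED | correct | error | correct |
| Correct decision 4 (CD4) | ED | correct | error | correct |
| False negative 2 (FN2) | ED | error | error | correct |

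With each term a share of all Table 2 patients, the change in 2.1 when urgency replaces service is

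(FP1 low + FP2 low + FN1 higher + FN2 higher) − (CD3 low + CD4 low + CD1 higher + CD2 higher).

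The protocol gives none of these shares, so neither sign nor size can be derived. Taking one cell alone, if low-urgency Correct decision 4 patients were an assumed 5%, 10% or 20% of the total, 2.1 would lose 5, 10 or 20 percentage points from that cell before any offset from the others. This is a gross movement, not an estimate of the effect.

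**Step 3: does the methods section settle the matter?** Only in part. It defines ED correctness as positive answers divided by all patients staying at the ED after triage. In Table 2 terms:

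- As written: (CD2 + FN2) / (FP2 + CD2 + CD4 + FN2).
- By Table 2 correctness: (CD2 + CD4) / (FP2 + CD2 + CD4 + FN2).

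For patients advised ED, a positive answer is False negative 2, an error. Suppose the advice were never wrong among patients staying at the ED, so FP2 = FN2 = 0. Table 2 gives (CD2 + CD4)/(CD2 + CD4) = 1. The written ratio gives CD2/(CD2 + CD4), which is 0 if every patient advised GPC complied (CD2 = 0). The written ratio therefore does not measure correctness across all patients at the ED.

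**The case against.** The strongest reply is that 2.1 is loose wording, in a sentence with a typing error, for the physician's evaluation defined elsewhere. Question 2 itself is about detecting a primary care patient, and the methods section describes correctness by service. If no urgency rating is collected, an urgency-based proportion cannot be computed at all. This reading is plausible, and it limits the likely harm. It does not remove the point: 2.1 states a reference that conflicts with Table 2, and an analyst who falls back on the methods section meets the ED ratio of step 3, which conflicts with Table 2 as well.

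A reader might go further and infer that low-urgency patients rightly kept at the ED will count as errors, so that 2.1 understates correctness by a definite amount. The documents do not support this. It requires a rule that low urgency means GPC, which the protocol never states. It follows one cell and ignores those that could move the other way, including False positives 1 and 2. Any percentage attached to it rests wholly on assumed shares.

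The objection that the scope is narrow also stands. The primary question does not use this reference, question 2.2 uses referrals, and the safety focus, False positive 1, is equated in the text with referral back to the ED.

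**Conclusion.** The conflict is real and worth correcting. Question 2.1 names urgency; Table 2 and the methods section use appropriate service; the plan's own allocation rules show that these differ; and no physician urgency item or mapping is described. If 2.1 were applied literally with some mapping from urgency to service, patients could be misclassified in both directions, with unknown net direction and size. The existence of the conflict rests on no assumption beyond reading the misspelt word as urgency. The consequences for individual cells depend on the mapping assumed in step 2. The point about the ED ratio follows from the protocol's own definitions. The concern is confined to secondary validity question 2.1.

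**What to change.** Reword 2.1 as the proportion (Correct decisions 1 to 4) / (all Table 2 cells). For patients seen at the ED, use the physician's answer to the question on service. For patients seen at the GPC, use referral to an ED: no referral is correct for those advised GPC, and referral is correct for those advised ED, as Table 2 implies.

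In the same edit, correct the ED ratio in Methodology for the medical aspect so that a positive answer counts as correct only for patients advised GPC and a negative answer only for patients advised ED.

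If a physician urgency rating is recorded, report it separately as a check on the MTS urgency code.

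The cost is one sentence in the research questions and a matching correction in the methods section, with no new data collection.

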# Hypotheses and Research questions

#### Medical aspect

Our primary hypothesis: the extended triage intervention will lead to a substantial increase in the proportion of patients seen by the GP.

Without the intervention, all study patients can be divided in three categories: seen by ED, seen by GPC and left without being seen (after the triage). By adding the compliance of the patient to the allocation advice we get the following table:

	Patient goes to GPC	Patient goes to ED	Left without being seen
Advice GPC	Compliant patient GPC	Non-compliant patient GPC	Left without being seen type 1
Advice ED	Non-compliant patient ED	Compliant patient ED	Left without being seen type 2

Table 1: patient categories

The proportion of study patients seen at the GPC is a combination of patients compliant to a GPC advice and patients not compliant to an ED advice. The latter category will probably be small.

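### Question 2.2 and the GPC correctness ratio use different denominators, and neither gives the share of GPC advice that was right among patients who followed it

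*Combined protocol and SAP*

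**What the plan says.** The Research questions list under Medical aspect (section 4) contains question 2.2: "What is the proportion of correct extended triage decisions with advice GP measured by the proportion of referrals within this category". The category it names is the set of decisions with GPC advice.

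Tables 1 and 2 in the same section show what that set holds:
- patients who went to the GPC (Correct decision 1 or False positive 1);
- patients who stayed at the ED, labelled "Non-compliant patient GPC" in Table 1 (Correct decision 2 or False positive 2 in Table 2);
- patients who left without being seen, type 1.

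Refusal is expressly allowed under A diagnostic Intervention: "Patients will have the right to refuse the advice of the nurse".

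The text before Table 2 says: "The way we will measure the correctness of the triage advice depends on whether the patient is compliant to this advice". Methodology for the medical aspect then gives two measures. The first covers the group "At the GPC (patients compliant to a GPC advice or non-compliant to an ED advice" and is "the ratio of patients referred to an ED to the total number of patients coming from the ED of AZ Monica". The second is for patients who stay: "At the ED (patients compliant to an ED advice or non-compliant to a GPC advice): the physician will answer the same question for all patients".

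On False positive 1, the text after Table 2 says: "This category is the same as the proportion of study patients allocated to the GP but referred back to the ED". This equates a cell of the table with a proportion and does not say clearly what the proportion is taken over.

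**The concern.** The safety-relevant quantity is simple: of the patients who were advised to go to the GPC and went, how many did the GPC have to send to an ED? The plan says False positive 1 is the category of most interest because of a possible safety risk, and it gives safety monitoring as one reason for a one-year study. The rate for that category should have one denominator, fixed before analysis.

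The plan offers two, and they differ in both directions. The question's own denominator is too wide on the compliance side, because it includes patients in whom a GPC referral cannot occur. The methods denominator is right on compliance but too wide on advice, because it includes ED-advised patients who went to the GPC anyway. The methods section also calls a referral ratio correctness, although for GPC-advised patients a referral marks an error. Two analysts following the plan in good faith could report different figures under the same label.

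**Working it through.** **Inputs.** The documents state no compliance rate, referral rate or target for question 2.2, so there is no figure to reproduce. The following are assumptions:
- c, the share of GPC-advised patients who reach the GPC: 40% to 95%;
- r, the referral rate among those patients: 5% or 10%;
- m, the share of GPC arrivals from this ED who had ED advice: 2% to 10%;
- q, the referral rate among those ED-advised arrivals: 30%.

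The target is False positive 1 / (Correct decision 1 + False positive 1) = r.

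**Rule A: question 2.2 read literally.** Referrals arise only in the share c, so the reported rate is c × r. Per 1,000 GPC advices with c = 0.60 and r = 0.10, 600 reach the GPC and 60 are referred. Then 60/600 = 10%, but 60/1,000 = 6%.

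| c | true r = 5% reads | true r = 10% reads |
|---|---|---|
| 0.40 | 2.0% | 4.0% |
| 0.60 | 3.0% | 6.0% |
| 0.80 | 4.0% | 8.0% |
| 0.95 | 4.75% | 9.5% |

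Leavers contribute little. The plan reports fewer than five per weekend after triage and 8,000 weekend presentations in 2016. That is 8,000/52 ≈ 154 per weekend, and 5/154 is under 3.3%. With the 15 expected exclusions removed, 5/139 is about 3.6%. The share among GPC-advised patients is not given. Any material dilution would come from refusers. It would grow if GPC advice from control weekends, which is recorded but not disclosed to patients, were pooled in.

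**Rule B: the GPC ratio in the methods section.** Only arrivals are counted, so the dilution in Rule A disappears. The pooled rate is (1 − m) × r + m × q. With r = 5% and q = 30%:
- m = 2%: 0.98 × 5% + 0.02 × 30% = 5.5%
- m = 5%: 0.95 × 5% + 0.05 × 30% = 6.25%
- m = 10%: 0.90 × 5% + 0.10 × 30% = 7.5%

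The distortion is m × (q − r). It vanishes if the two groups are referred equally often.

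**Meaning of a referral, by Table 2.** For a GPC-advised patient at the GPC, a referral is False positive 1, a nurse error. For an ED-advised patient at the GPC, it is Correct decision 3, a nurse success. The pooled numerator adds the two, so neither the ratio nor its complement is a proportion of correct decisions.

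**The case against.** The strongest reply is that a research question is not a scoring formula and that the scoring is set out elsewhere. Measurement is said to depend on compliance. The referral ratio is confined to patients who arrive at the GPC. Refusers are judged by the ED physician and fall into False positive 2 or Correct decision 2. Patients who leave are dropouts with no cell in Table 2, and question 5 addresses them. Questions 2.3 and 2.4 ask for all false positives and for type 1 false positives.

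Much of this stands. A reader might infer from question 2.2 that the plan scores refusers and leavers as correct, so that more refusals would make the advice look safer. The documents do not support that: no text assigns them to the correct cells, and the methods section judges refusers separately. The dilution under Rule A follows only if the question's sentence is applied literally.

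The reply does not remove the mismatch. The methods section does not say that its ratio answers question 2.2 or replaces the denominator there. Its ratio includes ED-advised patients, whereas question 2.2 is limited to GPC advice. It is also fair to say that the plan expects few patients to go to the GPC against ED advice, which limits the distortion under Rule B.

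**Conclusion.** The point holds as a denominator mismatch. The literal question and the methods ratio cannot both be the measure, and neither yields the share of right advice among patients who followed GPC advice.

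The possible size depends on which rule is used. Under the literal question, the referral rate shrinks by the factor c (10% reads as 6% at c = 60%). Under the methods ratio, 5% reads as 5.5% to 7.5% over the assumed range of m with q = 30%. All values of c, r, m and q are assumptions.

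A reader might also infer that correcting the measure must make GPC advice look worse. That does not follow. Compared with the literal question, correctness falls (94% to 90% in the example with c = 60% and r = 10%). Compared with the methods ratio, 1 minus the ratio rises (93.75% to 95% in the example with m = 5%) whenever ED-advised arrivals are referred more often.

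Severity is minor: this is a descriptive secondary question and the primary outcome is unaffected.

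**What to change.** 1. Define question 2.2 as Correct decision 1 / (Correct decision 1 + False positive 1). This is 1 minus the proportion referred to an ED among GPC-advised patients seen at the GPC in intervention weekends.
2. In Methodology for the medical aspect, split the GPC ratio by advice. State that a referral counts as an error after GPC advice and as a correct decision after ED advice.
3. Report Correct decision 2 / (Correct decision 2 + False positive 2) separately for intervention-weekend patients who refused GPC advice and stayed at the ED. The restriction keeps out control-weekend patients, who were never told the advice and so did not refuse it.
4. Give the count of patients who left without being seen, type 1, beside these ratios and in neither denominator.

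The cost is wording in two places. Advice, destination, referral and the ED physician's answer are already part of the planned data, so nothing new has to be collected. The reported figure may move in either direction, depending on which of the two stated denominators would otherwise have been used.
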